#### Platelet aggregation and bleeding risk

A role of SYK in platelet function has been demonstrated in literature [[R15-5470](#)]. Several platelet functions rely on SYK signalling (e.g. collagen receptor GPVI) but others are independent of SYK [[R16-5240](#)]. *In vitro* studies using human platelets demonstrated that at concentrations up to 100 µM, BI 894416 had no effect on extrinsic or intrinsic coagulation pathways. Also, BI 894416 did not inhibit ADP-induced platelet aggregation up to 100 µM. However, BI 894416 inhibited collagen- and arachidonic acid-induced platelet aggregation at 3 µM and 5 µM. However, platelet function as measured by bleeding time is not affected by a drug unless all the platelet pathways are inhibited due to redundancy within the system. Therefore, no risk for bleeding exists with regard to platelet inhibition unless a subject is also on another antiplatelet drug that blocks these other pathways. In line with this conclusion, data of previous trial 1371-0001 do not indicate any signs of an increased risk of bleeding.

*Risk mitigation and monitoring:* Use of any other concomitant drug that could reasonably inhibit platelet aggregation or coagulation (e.g. acetylsalicylic acid) will be prohibited (see Sections [3.3.3](#) and [4.2.2.1](#)). Adverse events will be monitored for any signs of bleeding or bleeding-related adverse events.

#### Bone density

SYK is reported to be involved in osteoclast differentiation, development and function. For details see the IB [[c03536505-04](#)]. In this trial, each subject is treated with two single doses of BI 894416. Due to comparatively slow turnover of bone tissue, no relevant effect on bone is expected due to two single-dose administrations with BI 894416 in this trial, and no specific monitoring of bone density is necessary or reasonable in this trial.

#### Mortality / morbidity in preclinical studies

Mortality / sacrifice due to morbidity occurred in CByB6F1 non-transgenic mice and in Wistar Han rats. Clinical signs preceding morbidity were similar in both rodent species and included respiratory changes (rapid, shallow, and/or labored breathing), decreased motor activity, ruffled fur, hunched or prostrate posture, eye changes (squinting, discharge) and/or hypothermia. One humane sacrifice due to overt neurotoxicity was done in one dog of the 3-day escalation study. For details see the current version of the IB [[c03536505-04](#)].

*Risk mitigation and monitoring:* Data of previous trial 1371-0001 indicate good safety and tolerability of BI 894416 at all investigated doses (single oral doses up to 70 mg). The dose of

Proprietary confidential information © 2019 Boehringer Ingelheim International GmbH or one or more of its affiliated companies

BI 894416 given in this trial is lower than doses given previously to healthy volunteers, and no increase of exposure of BI 894416 is expected when given with rifampicin. That means, BI 894416 plasma exposures expected in this trial are in the range measured previously in trial 1371-0001 and that were associated with good safety and tolerability. Moreover, subjects will be in-house at the trial site under close medical observation for 24 h after administration of BI 894416. Vital signs and ECGs will be measured during the trial, and subjects will be instructed to report AEs spontaneously and will be asked at pre-defined time points for AEs. In case of AEs in need of treatment, the investigator can authorise symptomatic therapy. In those cases, subjects will be treated as necessary and, if required, kept under supervision at the trial site or transferred to a hospital until all medical evaluation results have returned to an acceptable level.

### Neurotoxicity

In dog toxicology studies, acute adverse neurological effects with tremor and movement disorder assessed as dyskinesia (paresis / rigidity) were observed at high exposures (see IB [[c03536505-04](#)]). One dog was euthanized due to overt neurotoxicity in 3-day escalation study at 90 mg/kg/day. In dose escalation study in dogs with assessment of neurotoxicity [[n00245394](#)], all clinical signs of neurotoxicity were reversible with cessation of dosing. No structural changes were observed on histopathology. Peripheral nerve conduction velocity and EEG were unchanged. No specific mechanism causing the neurological effects in dogs has been elucidated. Therefore, it has not been determined whether the neurological changes are species specific; however, external expert review considered this is most likely a channelopathy specific to dog and not likely to occur in man (see IB).

*Risk mitigation and monitoring:* Subjects with relevant neurological disorder in the medical history are excluded from trial participation (see Section [3.3.3](#), criteria 7 and 22). Neurological examinations as described in Section [5.2.5.1](#) will be performed at screening, and subjects with clinically relevant findings in the neurological examination will be excluded from study participation (see Section [3.3.3](#), criterion 1). If necessary (investigator decision), unscheduled neurological examinations may be performed at any time during the trial. Relevant findings in the neurological examination during the trial will be reported as AEs. If necessary, subjects may be sent for further, more specific evaluation and treatment to a local neurologist.

### Genotoxicity, reproductive and developmental toxicity

Genetic toxicology results by weight of evidence indicate that BI 894416 is not mutagenic or clastogenic. In the 2-week repeat dose range finding study in male rats [[n00240179](#)], degeneration of spermatids of the testes was observed at  $\geq 400$  mg/kg/day, which is considered a secondary effect, related to overt toxicity and morbidity.

It is unknown whether BI 894416 or its metabolites are distributed into male semen. Theoretically there is therefore a risk for exposure of a study subject's female partner who is a woman of child bearing potential (WOCBP) to subtherapeutic exposures of BI 894416 or its metabolites via male semen. Developmental and reproductive studies have not yet been conducted, therefore the effect of subtherapeutic concentrations of BI 894416 or its metabolites with regards to embryofetal risk has not been explored so far.

Proprietary confidential information © 2019 Boehringer Ingelheim International GmbH or one or more of its affiliated companies

*Risk mitigation:* In order to address the risk of exposure of a subject's female WOCBP partner to BI 894416 or its metabolites via the subject's seminal fluid, subjects need to use barrier contraception (condom) or abstinence (see Section [3.3.3](#)).

### Phototoxicity

Subjects will be advised to avoid direct exposure to sun and UV light during the entire study (see Section [4.2.2.2](#)). Further protective measures would not be necessary given the low phototoxic potential of BI 894416.

### Potential effects on QT interval

Preclinical studies suggested no proarrhythmic potential or cardiovascular liability with BI 894416. However, statistical results of first-in-man trial 1371-0001 showed a most-likely dose- and concentration-dependent increase of QTcF interval. At gMean  $C_{max}$  of the 70 mg dose group, placebo- and baseline-corrected predicted mean QTcF increase was 5.9 ms (upper limit of the 90% CI was 10.5 ms). It is expected that plasma concentrations reached in current trial 1371-0005 are lower than the maximal plasma concentrations reached in trial 1371-0001.

*Risk mitigation:* Subjects with cardiovascular disorders (Section [3.3.3](#), exclusion criterion 5), subjects who used drugs that cause QT/QTc prolongation (Section 3.3.3, exclusion criterion 11), subjects that show a marked baseline prolongation of QT/QTc interval or any other relevant ECG finding at screening (Section 3.3.3, exclusion criterion 19), and subjects with a history of additional risk factors for Torsade de Pointes arrhythmia (Section [3.3.3](#), exclusion criterion 20) are excluded from trial participation. Moreover, subjects are in-house under close observation for 24 h following drug administration, and ECGs are done pre- and post-dose at the time points given in the [Flow Chart](#). Considering these risk-mitigating measures, the risks to subjects participating at trial 1371-0005 due to potential effects on QT interval are considered minimal.

#### 1.4.3.2 Risks related to rifampicin

Rifampicin will be dosed for a limited period of time, i.e. 7 days during the present study at a clinical standard dose of 600 mg once daily. Multiple dose-administration of rifampicin is commonly used in drug-drug interaction trials involving healthy subjects because it allows investigating the impact of administration of a strong CYP3A inducer on the pharmacokinetics of co-administered (investigational) drugs.

In previous trials in healthy volunteers performed by us, administration of rifampicin for up to 12 days was of acceptable safety and tolerability [[U09-1349-01](#), [U10-1328-01](#), [U12-1140-01](#), [U13-1478-01](#)]. A typical side effect after administration of rifampicin to healthy subjects is reversible chromaturia. The colour of the urine may vary between orange, dark, orange, red, red-brown, and brown. Rarely, rifampicin can cause disturbances of blood count, such as leukopenia, neutropenia or thrombopenia. Frequently, mild hypersensitivity reactions can occur. Severe hypersensitivity reactions are rare or very rare. Frequently, gastrointestinal

Proprietary confidential information © 2019 Boehringer Ingelheim International GmbH or one or more of its affiliated companies

symptoms are reported. Very frequent are increases of ALAT, ASAT, AP or gGT. Uncommon are icterus and hepatomegaly and acute hepatitis is very rare. A full listing of the reported side effects of rifampicin can be found in [R19-2541].

*Risk mitigation:*

- Safety and tolerability will be closely monitored during the trial, including regular assessment of adverse events and safety laboratory.
- Subjects will be instructed to report AEs spontaneously and will be asked at pre-defined time points for AEs. In case of AEs in need of treatment, the investigator can authorise symptomatic therapy. In those cases, subjects will be treated as necessary and, if required, kept under supervision at the trial site or transferred to a hospital until all medical evaluation results have returned to an acceptable level.
- Individual treatment will be stopped if pre-specified criteria are met (see Section 3.3.4.1). To account for the risk of rifampicin to very rarely cause acute hepatitis, an increase of ALAT and/or ASAT  $>2\times$  ULN triggers stopping of individual treatment of a subject.
- A thorough screening examination will ensure that only suitable healthy subjects will enter the study.
- Only subjects with liver enzyme values that do not exceed the ULN will be included into the study (see Section 3.3.3, criterion 25).

Considering these safety measures and taking into account the reported acceptable tolerability of rifampicin in healthy subjects, the planned administration of rifampicin does not represent an undue risk to healthy volunteers.

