7. Letters A, B, and C define different sets of safety laboratory examinations (see Section [5.2.3](#))
8. Unscheduled neurological examinations may be added at any time during the trial for individual volunteers or the whole treatment group, e.g., in case of neurological adverse events, if assessed as necessary by the investigator.
9. Within 15 min of next drug administration
10. Only urine drug screening and alcohol breath test
11. A blank urine sample (x) is to be obtained prior to administration of trial medication. Other urine samples are to be collected over the stated post-dose intervals (◀—|—|▶) 0-4, 4-8, 8-12, and 12-24 h.
12. Pharmacogenetic samples will be collected at Day 1 prior to administration.

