#### 3.3.4.1 Discontinuation of trial treatment

An individual subject will discontinue trial treatment if:

1. The subject wants to discontinue trial treatment, without the need to justify the decision
2. The subject has repeatedly shown to be non-compliant with important trial procedures and, in the opinion of both, the investigator and sponsor representative, is not willing or able to adhere to the trial requirements in the future.
3. The subject needs to take concomitant medication that interferes with the investigational medicinal product or other trial treatment
4. The subject can no longer receive trial treatment for medical reasons (such as surgery, adverse events [AEs], or diseases)
5. The subject has an elevation of AST and/or ALT  $\geq 2$ -fold ULN and/or needs to be followed up according to the DILI checklist provided in the ISF
6. The subject experiences a drug-related AE of severe intensity or a serious AE

In addition to these criteria, the investigator may discontinue subjects at any time based on his or her clinical judgment.

Even if the trial treatment is discontinued, the subject remains in the trial and, given his agreement, will undergo the procedures for early treatment discontinuation and follow up as outlined in the [Flow Chart](#) and Section [6.2.3](#).

Proprietary confidential information © 2019 Boehringer Ingelheim International GmbH or one or more of its affiliated companies

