#### 4.1.4 Drug assignment and administration of doses for each subject

This trial is a one-way crossover study. All subjects will receive the 2 treatments in fixed order. The treatments to be evaluated are outlined in Table [4.1.4: 1](#) below.

Table 4.1.4: 1 Dosage and treatment schedule

Treatment period	Treatment	Substance	Formulation	Unit strength	Dosage	Total dose
1	R (Reference)	BI 894416	Tablet	25 mg	2 tablets as single dose on Day 1	50 mg
2	T (Test)	Rifampicin	Film-coated tablet	600 mg	1 tablet q.d on Days -7 to -1	4200 mg
		BI 894416	Tablet	25 mg	2 tablets as single dose on Day 1	50 mg

Administration of BI 894416 will be performed after subjects have fasted overnight; fasting is to start no later than 10 h before the scheduled dosing.

For administrations of rifampicin, subjects are advised to fast for at least 2 hours before and at least 30 minutes after drug administrations.

The investigator (or authorised designee) will administer the trial medication as an oral dose together with about 240 mL of water to subjects who are in a standing position. For drug administration, the so-called four-eye principle (two-person rule) should be applied. For this, one authorised employee of the trial site should witness the administration of trial medication, and – if applicable – its preparation (e.g. reconstitution), if correct dosage cannot be ensured otherwise.

For restrictions with regard to diet, see Section [4.2.2.2](#).

Subjects will be kept under close medical surveillance until 24 h after BI 894416 administration. During the first 4 h after BI 894416 administration, subjects are not allowed to lie down (i.e. no declination of the upper body of more than 45 degrees from upright posture).

The first rifampicin administration will be followed by a 2-hour post-administration in-house observation period.

The administrations of BI 894416 will be separated by a wash-out phase of at least 10 days.

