#### 5.2.3 Safety laboratory parameters

For the assessment of laboratory parameters, blood and urine samples will be collected by the trial site at the times indicated in the Flow Chart. For safety laboratory parameter sets A and B subjects should be fasted for at least 10 h. For safety laboratory parameter set C, fasting is not required. For retests, at the discretion of the investigator or designee, overnight fasting is not required.

The parameters that will be determined are listed in Tables [5.2.3: 1](#) and [5.2.3: 2](#). Reference ranges will be provided in the ISF, Section 10.

Manual differential white blood cell count or urine sediment examinations will only be performed if there is an abnormality in the automatic blood cell count or in the urinalysis, respectively.

Proprietary confidential information © 2019 Boehringer Ingelheim International GmbH or one or more of its affiliated companies

Table 5.2.3: 1

Routine laboratory tests

Functional lab group	BI test name [comment/abbreviation]	A 	B 	C 
Haematology	Haematocrit Haemoglobin Red Blood Cell Count/Erythrocytes White Blood Cells/Leucocytes Platelet Count/Thrombocytes (quant)	X X X X X	X X X X X	X X X X X
Automatic WBC differential, relative	Neutrophils/Leukocytes; Eosinophils/Leukocytes; Basophils/Leukocytes; Monocytes/Leukocytes; Lymphocytes/Leukocytes	X	X	X
Automatic WBC differential, absolute	Neutrophil, absol.; Eosinophils, absol.; Basophils, absol.; Monocytes, absol.; Lymphocytes, absol.	X	X	X
Manual differential WBC (if automatic differential WBC is abnormal and clinically relevant in the opinion of the investigator)	Neut. Poly (segs); Neut. Poly (segs), absol.; Neutrophils Bands; Neutrophils Bands, absol.; Eosinophils/Leukocytes; Eosinophils, absol.; Basophils/ Leukocytes; Basophils, absol.; Monocytes/ Leukocytes; Monocytes, absol.; Lymphocytes/Leukocytes; Lymphocytes, absol.			
Coagulation	Activated Partial Thromboplastin Time Prothrombin time – INR (International Normalization Ratio)	X X	X X	-- --
Enzymes	AST [Aspartate transaminase] /GOT, SGOT ALT [Alanine transaminase] /GPT, SGPT Alkaline Phosphatase Gamma-Glutamyl Transferase	X X X X	X X X X	X X X X
Hormones	Thyroid Stimulating Hormone	X	--	--
Substrates	Glucose (Plasma) Creatinine Bilirubin, Total Bilirubin, Direct Protein, Total C-Reactive Protein (Quant)	X X X X X X	X X X X X X	-- -- X X -- --
Electrolytes	Sodium Potassium	X X	X X	-- --

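### Do two wordings of the liver-enzyme stopping threshold, and a single liver sample during rifampicin dosing, defeat the stopping rule?

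*Protocol*

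**What the plan says.** **Threshold.** Protocol Section 1.4.3.2 lists the measures that contain rifampicin's risks. It says "Individual treatment will be stopped if pre-specified criteria are met (see Section 3.3.4.1"), and then that an ALAT and/or ASAT increase ">2\times$ ULN triggers stopping of individual treatment of a subject". That is strictly above twice ULN. Criterion 5 of Section 3.3.4.1 discontinues trial treatment for AST and/or ALT "\geq 2$ -fold ULN and/or needs to be followed up according to the DILI checklist provided in the ISF". That is at or above twice ULN, with a second trigger added.

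**Dosing and sampling.** Table 4.1.4: 1 gives rifampicin as "1 tablet q.d on Days -7 to -1", 4200 mg in total. At the Day -7 admission, Flow Chart footnote 10 limits testing to "Only urine drug screening and alcohol breath test". The only safety laboratory between the first and last rifampicin dose is set C at -38:00 on Day -2, which footnote 9 times as "Within 15 min of next drug administration". Table 5.2.3: 1 includes liver enzymes ("AST [Aspartate transaminase] /GOT, SGOT ALT [Alanine transaminase] /GPT, SGPT") in sets A, B and C. Set B follows at -2:00 on Day 1 of period 2, at 24:00, and at the end-of-trial visit.

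**The concern.** Section 1.2.2 describes liver enzyme elevations as very common with rifampicin. Sections 1.4.3.2 and 1.4.4 accept that risk partly because enzymes are measured and individual stopping criteria exist. A stopping rule written two ways invites inconsistent handling of a subject on the boundary. Because the rule ends trial treatment, it would also decide whether that subject supplies a test-period PK profile.

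The timing looks worse. If the only liver sample during dosing is drawn as the sixth dose is given, most of the rifampicin has been taken before anyone can act on a result. That seems thin beside a text that speaks of close monitoring and regular laboratory checks.

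**Working it through.** **1. Dose count.** The Flow Chart's rifampicin times are -158, -134, -110, -86, -62, -38 and -14 h relative to BI 894416. That is 7 doses × 600 mg = 4200 mg, which reproduces the total in Table 4.1.4: 1.

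**2. Position of the Day -2 sample.** Doses are 24 h apart, so the dose number at -38 h is (158 - 38)/24 + 1 = 6. Footnote 9 allows at most 15 min between sample and dose. I assume that the result is not back before dose 6. Then 6 × 600 = 3600 mg (86%) is given before any scheduled result from the dosing interval, and 600/4200 = 14% remains.

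**3. What the result can still stop.** Set C is 38 - 14 = 24 h before dose 7 and 38 h before BI 894416. The documents state no laboratory turnaround, so the range is:

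| Turnaround of set C | Rifampicin doses that can be withheld | Period 2 BI 894416 dose can be withheld |
|---|---|---|
| under 24 h | 1 (dose 7) | yes |
| 24 to 38 h | 0 | yes |
| over 38 h | 0 | not from this sample |

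The rule in Section 3.3.4.1 stops trial treatment as a whole, so the last column counts.

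**4. Later samples.** Set B on Day 1 falls 14 - 2 = 12 h after dose 7 and before BI 894416. Set B at 24:00 falls 24 + 14 = 38 h after dose 7. Both lie within the 6-day (144 h) rifampicin residual effect period of Section 1.2.3. The Day 1 pre-dose sample also lies in the rifampicin-alone interval of Protocol Section 7.3.4 and SAP Table 6.1: 2. Set C is therefore the only scheduled liver sample between the first and last dose, but not the only one under rifampicin's influence. The Day 1 sample cannot avert a rifampicin dose, and could avert BI 894416 only if read within about 2 h.

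**5. The two thresholds side by side.** Let x be the enzyme value divided by ULN.

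| x | Section 1.4.3.2 | Section 3.3.4.1 |
|---|---|---|
| below 2 | no trigger | no trigger |
| exactly 2 | no trigger stated | trigger |
| above 2 | trigger | trigger |

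The texts part at one value. Section 1.4.3.2 does not say that a subject at exactly 2 continues; it refers the reader to Section 3.3.4.1 for the criteria.

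**6. The DILI-checklist trigger.** Under Section 5.2.6.1.4 the laboratory findings that call for the checklist are AST and/or ALT at least 3-fold ULN with bilirubin at least 2-fold ULN, or aminotransferases at least 10-fold ULN. Both exceed 2-fold, so they are already caught under either wording. The extra clause adds no further enzyme threshold in practice.

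**7. PK consequence.** Section 7.7 enters 16 subjects, allows up to 4 that are not PK-evaluable, and computes precision on 12. A profile lost because a value sat exactly on the boundary would come out of that allowance.

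**The case for a change.** The best case for acting is that an individual stopping rule should read the same wherever it appears, above all where one section cites the other. The benefit-risk argument put to ethics committees and authorities leans on it. With no liver sample at the Day -7 admission, the last scheduled one before rifampicin is set B at 24 h in period 1. At the minimum 10-day washout that is 240 - 158 - 24 = 58 h before the first dose, and no maximum washout is given. Scheduled sampling can then spare at most one rifampicin dose in seven.

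The arithmetic stands, and so does the mismatch in symbols. The inference that the rule cannot work does not. No section promises a liver result before any particular rifampicin dose, or that the rule will spare a given share of doses, so schedule and text do not contradict each other. Nor does the mitigation rest on one sample:

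- subjects with enzymes above ULN at screening are excluded (criterion 25);
- adverse events are asked about at the ambulatory rifampicin visits;
- retests are allowed (Section 5.2.3);
- symptoms of hepatic injury lead to liver tests, unscheduled if need be (Section 5.2.6.1.4);
- the investigator may discontinue a subject at any time (Section 3.3.4.1).

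Whether another sampling time would serve better is a clinical trade-off. The documents give no time course for enzyme elevations from which to settle it.

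**Conclusion.** No change to the design, schedule or analysis follows. What remains is a clerical slip: strictly above in Section 1.4.3.2, at or above in Section 3.3.4.1. The passages must be reconciled to the same wording when the text is next edited, and which wording applies is for the sponsor's clinical team. The slip can matter only for a value exactly at 2.00 times ULN. How likely that is cannot be computed, because the documents give neither the reference limits nor the reporting units.

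The timing is a fact worth knowing rather than an error. The scheduled Day -2 sample can avert at most the seventh rifampicin dose (14% of the total) and the second BI 894416 dose. This assumes that its result arrives after dose 6 but within 24 h for the former, or within 38 h for the latter. The geometric mean ratios, their confidence intervals and the planned precision do not depend on either point.
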